2. Admission to the **Intensive Care Unit (ICU) for more than 48 hours**.
3. Availability of **chest CT imaging data**.

Exclusion Criteria

1. Patients aged <18 years.
2. Patients with incomplete medical records.
3. Absence of chest CT imaging or presence of technically inadequate/uninterpretable chest CT images.

Sample Size and Data Partitioning

This study is designed as a multicenter, large-sample, retrospective observational study and plans to include a total of 400 patients with ARDS who meet the eligibility criteria. Of these, 300 cases will be contributed by the primary institution and Sub-center 1, and 100 cases by Sub-center 2.

The study does not involve conventional experimental or control groups. Instead, cases will be partitioned into three datasets according to the model development workflow:

Training set: 276 cases (approximately 80% of the combined cases from the primary institution and Sub-center 2), obtained through stratified random sampling to preserve the distribution of mild, moderate, and severe ARDS;

Internal validation set: 69 cases (approximately 20% of cases from the same two centers), used to monitor overfitting and optimize model hyperparameters;

External test set: 55 cases, all derived from Sub-center 1 and entirely independent of the model development process, used to evaluate model generalizability.

Primary Outcome Measures

The primary outcomes of this study focus on the overall effectiveness of the proposed AI-based framework across three key clinical tasks:

(1) Accuracy of ARDS severity classification, defined as the agreement between model-predicted ARDS severity (mild, moderate, or severe) and the reference clinical classification based on the 2023 global ARDS criteria, assessed using chest CT images obtained within 24 hours of ICU admission;

(2) Treatment plan matching rate, defined as concordance between model-recommended and actual clinical management across five intervention modalities (mechanical ventilation, high-flow oxygen therapy, non-invasive ventilation, prone positioning, and neuromuscular blockade), evaluated at the time of index chest CT acquisition;

(3) Accuracy of 28-day in-hospital mortality prediction, defined as the ability of the model to predict all-cause in-hospital mortality within 28 days of ICU admission.

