These three outcomes collectively reflect the overall effectiveness of the model within a closed-loop framework encompassing disease stratification, treatment recommendation, and prognosis prediction.

Secondary Outcome Measures

Secondary outcomes include comparative performance improvement of the proposed model over commonly used baseline AI models; calibration performance of mortality prediction; interpretability analyses based on imaging-derived and clinical feature contributions; and assessment of the association between treatment concordance and 28-day in-hospital mortality using multivariable regression models.

Research procedures

1. Data collection

(1) Demographic and Baseline Clinical Data

Age, sex, body mass index (BMI), comorbidities (including chronic kidney disease, coronary artery disease, hypertension, diabetes, liver cirrhosis, HIV infection, etc.), primary etiology of ARDS, and receipt of mechanical ventilation, high-flow nasal oxygen therapy, or ECMO. BMI is calculated as weight (kg) divided by height squared (m^2).

(2) Physiologic Parameters

Body temperature (T), heart rate (HR), respiratory rate (RR), peripheral oxygen saturation (SpO_2), and mean arterial pressure (MAP).

(3) Laboratory Parameters

pH, partial pressure of arterial oxygen (PaO_2), fraction of inspired oxygen (FiO_2), partial pressure of arterial carbon dioxide (PCO_2), lactate (Lac), platelet count (PLT), white blood cell count (WBC), hemoglobin (Hb), serum creatinine, C-reactive protein (CRP), procalcitonin (PCT), international normalized ratio (INR), B-type natriuretic peptide (BNP), and interleukin-6 (IL-6).

(4) Ventilator or High-Flow Oxygen Parameters

Positive end-expiratory pressure (PEEP), tidal volume (TV), plateau pressure (Pplat), and flow rate (FLOW).

(5) Other Clinical Scores

Sequential Organ Failure Assessment (SOFA) score and Acute Physiology and Chronic Health Evaluation II (APACHE II) score.

2. CT Equipment and Scanning Parameters

Chest CT images included in this study were acquired from two CT scanners with the following parameters:

CT1 (64-slice): Manufacturer: Philips; Model: Brilliance; Tube voltage: 120 kV; Tube current: 1000 mA; Slice thickness: 5 mm; Slice interval: 5 mm; Pitch: 0.789:1.

CT2 (128-slice): Manufacturer: United Imaging; Model: uCTR760; Tube voltage: 120 kV; Tube current: 1000 mA; Slice thickness: 5 mm; Slice interval: 5 mm; Pitch: 0.984:1.

3. Quantitative Assessment of ARDS

Preliminary Image Processing

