The sample size was preliminarily estimated using the event-per-variable principle. The mortality prediction component is designed to include no more than 15 candidate predictors in the final multivariable logistic regression model. Following the commonly accepted criterion of at least 10 outcome events per predictor, a minimum of 150 death

events is required to ensure model stability and interpretability. Based on historical data from the participating centers, the in-ICU mortality rate among patients with ARDS is approximately 37.5%. Accordingly, the total target sample size for this study is estimated to be approximately 400 patients.

Statistical Analysis Plan

All eligible cases will be stratified and randomly sampled at an 8:2 ratio within Shanghai General Hospital and its affiliated centers to form the model training set and internal validation set. Cases from an additional participating center will be reserved as an independent external test cohort.

Model performance will be evaluated for three predefined tasks: ARDS severity classification, treatment strategy prediction, and mortality risk prediction. Performance metrics will include accuracy, balanced accuracy, area under the receiver operating characteristic curve (AUC), precision–recall curve analysis, and the Brier score. During model development, five independent repeated experiments will be conducted, and performance will be reported as mean values with standard deviations.

For comparative performance assessment, results from the five independent experiments will be compared using two-sided Wilcoxon rank-sum tests, with a significance threshold of 0.05. Different levels of statistical significance will be denoted using conventional symbols (e.g., “*”, “**”) corresponding to predefined P-value ranges.

To assess the association between model outputs and clinical outcomes, model-recommended intervention sets will first be encoded for agreement with actual clinical management. These agreement variables will then be incorporated into multivariable logistic regression models together with six imaging-derived anatomical features (e.g., diaphragmatic height, lung volume). Adjusted odds ratios with 95% confidence intervals will be reported, and a two-sided P value <0.05 will be considered statistically significant.

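### The single secondary question on concordance and death is tested through an unstated number of agreement variables, each at 0.05, with no overall test

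*Combined protocol and SAP*

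**What the plan says.** Secondary Outcome Measures words the outcome as a single association: "assessment of the association between treatment concordance and 28-day in-hospital mortality using multivariable regression models".

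The fourth paragraph of the Statistical Analysis Plan gives the method. First, "model-recommended intervention sets will first be encoded for agreement with actual clinical management". Then, "These agreement variables will then be incorporated into multivariable logistic regression models together with six imaging-derived anatomical features". The decision rule follows directly: "Adjusted odds ratios with 95% confidence intervals will be reported, and a two-sided P value <0.05 will be considered statistically significant".

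The agreement variables, the models and the odds ratios are all plural. The plan does not say how many agreement variables there are, whether each describes one modality or a whole recommended set, or which patients are analysed. The only count in the documents that bears on this is under Primary Outcome Measures, item 2, where the matching rate is defined across "five intervention modalities (mechanical ventilation, high-flow oxygen therapy, non-invasive ventilation, prone positioning, and neuromuscular blockade". Neither the protocol text nor the SAP names a joint test, a lead concordance term, a testing order, a multiplicity adjustment or an exploratory status for this analysis.

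**The concern.** One question is answered by several coefficients, and any one of them below 0.05 would allow the authors to report that concordance is associated with mortality. The nominal 5% applies to each coefficient, not to the question.

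This is the only specified analysis that relates agreement with the model's recommendations to death, and the Primary Objective is to help guide therapeutic strategy. A chance odds ratio for one modality could be read as support for following the model on that treatment. The data already exist, so a coding and claim rule left open now can be settled after results are seen. The problem is separate from confounding.

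**Working it through.** **Inputs from the documents**
- Two-sided 0.05 per test, unadjusted; six anatomical features (Statistical Analysis Plan).
- Five modalities (Primary Outcome Measures, item 2).
- About 400 patients and 37.5% in-ICU mortality (Sample size estimation).
- Training and internal validation sets of 276 and 69, together 345; external test set of 55 (Sample Size and Data Partitioning).

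**Assumptions, not in the documents**
- k, the number of agreement variables, varied from 1 to 5.
- In the simulations, 69% or 75% agreement per modality, with in-ICU mortality standing in for 28-day in-hospital mortality.

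**The plan's own figure.** The plan states no overall error rate for this analysis. Its sample size does reproduce: 15 predictors × 10 events = 150 deaths, and 150 / 0.375 = 400.

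**Step 1: independent tests.** The chance of at least one false association among k tests is 1 − 0.95^k. For a false benefit only (odds ratio in the favourable direction) it is 1 − 0.975^k.

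| k | Either direction | False benefit only |
|---|---|---|
| 1 | 5.0% | 2.5% |
| 2 | 9.8% | 4.9% |
| 3 | 14.3% | 7.3% |
| 4 | 18.5% | 9.6% |
| 5 | 22.6% | 11.9% |

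Whatever the correlation, five tests that each hold their level cannot exceed 5 × 0.05 = 25%.

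**Step 2: correlated test statistics, k = 5.** The either-direction rate is 20.9% at correlation 0.3, 18.2% at 0.5, 14.8% at 0.7 and 10.2% at 0.9.

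**Step 3: the fitted model under no association.** Five binary agreement terms and six noise features were fitted to 3,000 simulated datasets of n = 400, with 37.5% mortality and 75% agreement. The Monte Carlo standard error near 23% is √(0.23 × 0.77 / 3000) = 0.8 points.

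| Latent correlation of agreement | Any of 5 terms | False benefit | Joint 5-df likelihood-ratio test |
|---|---|---|---|
| 0 | 24.2% | 13.3% | 6.2% |
| 0.5 | 23.7% | 13.6% | 6.8% |
| 0.8 | 20.4% | 11.6% | 5.1% |

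The false-benefit column averages (13.3 + 13.6 + 11.6) / 3 = 12.8%, close to the 11.9% from the formula. With 69% agreement and n = 345 (1,500 datasets per setting), any of five gave 21.9% to 24.5% and the joint test 5.2% to 6.2%.

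**Step 4: other readings of the plan, n = 400 (1,000 datasets).**
- One model per agreement variable: 23%, 21% and 17.5% at latent correlation 0, 0.5 and 0.8.
- Three respiratory-support modalities treated as mutually exclusive (a further assumption): about 20%.
- A single concordance score: 4.5% to 5.6%.

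**Step 5: if the analysis set were the 55 external cases.** Expected deaths are 55 × 0.375 = 20.6, or 20.6 / 11 = 1.9 per model term. Any of five gave 16% to 27%. The joint likelihood-ratio test itself rejected in 12% to 16%, so it does not hold its level at that size.

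**The case against.** **The number of variables is not known.** Five comes from the definition of a different outcome, the matching rate, while the SAP paragraph speaks of encoding intervention sets. Two variables, such as exact match and proportion matched, would fit the plural. This stands. A reader might infer that 23% is a property of the plan, but the documents do not support that. It holds only for one variable per modality with test statistics that are not strongly correlated.

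**The 23% counts both directions.** This also stands. A reader might take it as the chance of a false survival benefit, which is about half as large.

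**The anatomical features.** A reader might infer from the blanket threshold that each of the six is also a concordance claim and add them to the count. The secondary outcome concerns treatment concordance only, and entering the features alongside the agreement variables to obtain adjusted odds ratios fits a covariate role. They do not belong in the error rate.

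**Strict error control is not obligatory.** This is a secondary outcome in a retrospective model-development study whose project name begins with the word Exploration, and odds ratios with intervals are ordinary reporting in such work. That is fair, and it means a formal correction across modalities need not be demanded. But this analysis carries no exploratory label, and the plan chose to declare significance, so the rule for doing so has to be defined.

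**Conclusion.** The point holds in conditional form. The plan gives one secondary question several unadjusted tests at 0.05, with no overall test, and leaves the number and coding of the variables open. The resulting chance of at least one false association is about 10% for two independent variables and up to about 23% for five. With five, a false benefit alone is about 12–13%, against 2.5% for one two-sided test. Strong correlation between the test statistics would lower these rates, and a single concordance variable would bring the overall rate back to 5%. The absence of an overall test is plain from the text. The size rests on the assumed number of variables, their correlation and the proxy mortality rate. This should be corrected, but it does not touch the three primary outcomes.

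**What to change.** In the fourth paragraph of the Statistical Analysis Plan:

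1. State how many agreement variables there are, how each is coded, and which analysis set is used.
2. Make the test of this secondary outcome one pre-specified test at two-sided 0.05: either a joint likelihood-ratio test of all agreement terms in one named model, or the test of one pre-specified overall concordance variable.
3. Report modality-specific odds ratios with 95% intervals as exploratory.
4. State that the six anatomical features are adjustment covariates and carry no significance claim.

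The choice in item 2 should follow the analysis set. The joint test is close to its nominal level at n = 345 to 400 but not at n = 55, where any large-sample test should have its error rate checked before it is adopted.

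The cost is a few sentences and, for the joint test, one extra comparison using the same fitted model. No new data are needed. The downside is a modest loss of power to claim an association for a single modality.

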For mortality risk prediction, ARDS severity classification and treatment strategy information will be sequentially added to the input features to evaluate their incremental impact on balanced accuracy and Brier score. Model calibration and discrimination will be assessed using calibration curves and precision–recall curves. In addition, least absolute shrinkage and selection operator (LASSO) regression will be applied to all structural, pathological, and intervention-related variables, and standardized coefficients will be extracted to facilitate interpretation of key risk-driving factors across different ARDS severity strata.

Ethics and Informed Consent

This study is a multicenter, retrospective, observational study involving the secondary use of previously collected clinical and imaging data. The study protocol, informed consent materials (where applicable), and all subject-related documents were submitted to the institutional ethics committee and approved prior to study initiation. The study will be conducted in accordance with the Declaration of Helsinki and relevant national and institutional regulations.

The investigators will submit periodic progress reports to the ethics committee as required. Any protocol amendments or changes related to informed consent procedures will be reported to and approved by the ethics committee before implementation, unless such changes are necessary to eliminate an immediate and direct risk to participants, in which case the ethics committee will be notified promptly. The ethics committee will also be informed in writing upon study suspension or completion.

Given the retrospective nature of the study and the use of existing identifiable data without commercial interest, a partial waiver of informed consent was approved by the ethics committee. For participants who can be successfully contacted, investigators will first provide oral information about the study and document the communication. If participants or their legal representatives subsequently return for clinical follow-up, written informed consent will be obtained. For participants who cannot be contacted, the requirement for informed consent is waived in accordance with ethical and regulatory guidelines.

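### Calibration of mortality prediction is a secondary outcome but is assessed only by curves, with no calibration-in-the-large, slope or patient-level interval, and 55 external cases cannot make a curve reliable

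*Combined protocol and SAP*

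**What the plan says.** Secondary Outcome Measures lists "calibration performance of mortality prediction" without a measure or target. The Statistical Analysis Plan gives the method: "Model calibration and discrimination will be assessed using calibration curves", plus precision–recall curves, which do not measure calibration. It states no grouping or smoothing rule and does not name the dataset for the curve.

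The Brier score appears twice in the Statistical Analysis Plan: in the general list of performance metrics, and as a measure of what severity and treatment information add to the mortality model. The only uncertainty stated for performance is a standard deviation over five repeated experiments during model development.

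Sample Size and Data Partitioning defines the set meant for generalizability: "External test set: 55 cases, all derived from Sub-center 1 and entirely independent of the model development process". The modelled outcome, under Primary Outcome Measures, is to "predict all-cause in-hospital mortality within 28 days of ICU admission". The only mortality figure is under Sample size estimation: "the in-ICU mortality rate among patients with ARDS is approximately 37.5"%.

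**The concern.** A model developed at two centres and moved to a third can predict risks that are too high or too low overall, or too spread out. Calibration-in-the-large (observed minus mean predicted risk) measures the first fault and the calibration slope measures the second. The plan has neither. An SD over five reruns describes how much the fitting process varies. It does not say how far the result might differ in another 55 patients from the same hospital.

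The study could therefore reach its calibration outcome with a plot and no statement of how much miscalibration the data exclude. At this sample size a plot can look acceptable or poor by chance, and the reader would have no means of telling which.

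**Working it through.** **The plan's own figure.** Sample size estimation allows "no more than 15 candidate predictors in the final multivariable logistic regression model" and requires "at least 10 outcome events per predictor": 15 × 10 = 150 deaths, and 150 / 0.375 = 400 patients. This reproduces. It concerns model fitting in all 400 and gives no precision for validation.

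**The external set.** The partition in Sample Size and Data Partitioning fits its centre counts. If Sub-center 1 supplies 55, the primary institution supplies 300 − 55 = 245; with Sub-center 2, 245 + 100 = 345 = 276 + 69; and 345 + 55 = 400. Expected external deaths: 55 × 0.375 = 20.6, about 21. The 37.5% is in-ICU mortality, used as a proxy for 28-day in-hospital death.

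**Precision of a curve.** The 95% half-width of an observed proportion is 1.96 × √(p(1 − p)/n), with p = 0.375:

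| Patients | 95% half-width |
|---|---|
| 18.3 (thirds of 55) | 22 points |
| 11 (fifths) | 29 points |
| 5.5 (tenths) | 40 points |
| 55 (all) | 12.8 points |

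The plan gives no grouping, so these rows are illustrations. A uniform shift moves every point of the curve, so one group's interval is not the whole story. But even with all 55 patients pooled, a 10-point gap lies inside ±12.8 points.

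**Brier score, observed minus expected, and slope.** These come from simulation at n = 55 with logit-normal true risks. The documents give no AUC, so the AUC is assumed. Central scenario, mortality 37.5% and AUC about 0.79:

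- Well calibrated: Brier 0.175, sampling SD 0.026.
- Every risk raised on the logit scale so that the mean is 10 points too high: Brier 0.186, a rise of 0.011, or 0.011/0.026 = 0.42 SD.
- Predictions too extreme (true slope 0.6): Brier 0.184, a rise of 0.009, or 0.35 SD.
- Even against the 95th percentile for a calibrated model, which would be unknown in practice, the Brier score singles out these errors in only about 7–14% of samples.
- Observed minus expected has an SD of 5.5 points (95% half-width 1.96 × 5.5 = 10.8) and detects the 10-point error in about 40%. The slope test detects the slope of 0.6 in about 49%.

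Range over AUC 0.72 to 0.84 and mortality 25% to 50%:

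| Quantity at n = 55 | Range |
|---|---|
| Rise in Brier score, 10-point overstatement | 0.010–0.013 |
| Sampling SD of Brier score | 0.022–0.028 |
| Detection by observed minus expected | 37–49% |
| Detection of slope 0.6 by slope test | 32–54% |

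**Sensitivity to the split.** The image-processing text under Quantitative Assessment of ARDS describes a 60/20/20 random split. That implies a test set of 0.20 × 400 = 80, where detection of the 10-point error by observed minus expected is about 49–65%.

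**The case against.** The strongest reply is that the limit is the sample size, not the tools. The proposed statistics also miss the 10-point error in about 60% of samples in the central scenario. By the simple formula, 80% power would need (1.96 + 0.84)² × 0.375 × 0.625 / 0.10² ≈ 184 patients. This stands: the change makes imprecision visible and does not remove it.

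It is also fair that the plan states no deciles, does not give the Brier score the job of measuring calibration, and does not say that the curve will be drawn in the external set. No curve was simulated here; the case against it rests on the group and pooled intervals. The external set is taken as the relevant one because the plan names it for generalizability. The Brier figures show only that the score cannot fill the gap, not that the plan misuses it.

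A reader might infer that the study will declare good calibration on weak evidence, or that the added statistics would reliably catch a 10-point error. The documents support neither: they set no acceptance limit and announce no such claim, and detection stays below one half or close to it.

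Finally, calibration is one of several secondary outcomes, and nothing in the plan forbids adding these measures. That lowers the severity but does not answer the point.

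**Conclusion.** The concern holds as a gap in how a secondary outcome is defined. Calibration has no numerical measure and no patient-level interval, and in 55 external cases a curve cannot reliably show a 10-point error in mean risk. The Brier score does not compensate, since the error moves it by about half a sampling SD or less. Adding calibration-in-the-large and slope raises detection to roughly a third to a half. Its main value is an interval that states which miscalibration is excluded.

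The conclusion rests on 55 external cases, on in-ICU mortality as a proxy (it is stable from 25% to 50%), and on assumed AUCs and a logit-normal spread of risks. Severity is minor to moderate; no primary outcome is affected.

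**What to change.** In the mortality paragraph of the Statistical Analysis Plan, define the calibration outcome as:

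- (a) observed minus mean predicted 28-day in-hospital mortality; and
- (b) the calibration slope, from a logistic regression of death on the logit of predicted risk.

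Give each a 95% CI that reflects sampling of patients, in the external test set (Sub-center 1). Keep the curve as a descriptive plot and base any statement about calibration on (a) and (b). Label any estimate from the primary institution or Sub-center 2 as apparent, not validated, because those centres supply the training and tuning cases. Reconcile the 60/20/20 split with the 276/69/55 partition, so that the test set is fixed before analysis.

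The cost is a few lines of text and simple calculations on predictions the study will already have. The downside is wide intervals, about ±11 points for mean risk, so any calibration claim will be weaker.

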The proposed lung-segmentation DL model will accept lung-masked CT images as input (images cropped, masked, and rescaled to include the whole lung and lesions). The model outputs segmentation masks for left and right lungs, lobes, bronchopulmonary segments, and lesion types including ground-glass opacities (GGO), consolidation, and atelectasis. Anatomically, there are typically 18–20 bronchopulmonary segments; because segment-level granularity can complicate

downstream analysis, we will simplify segmental mapping into four bilateral segments and define 11 lung regions for analysis: right upper, right upper-middle, right lower-middle, right lower, whole right, left upper-middle, left lower-middle, left lower, whole left, and whole lung. By computing the proportion of lesion volume in each lung region, we will derive a structured set of imaging features reflecting regional lung involvement.

Interpretable Severity Assessment

Because segmentation results provide the primary evidence for severity assessment, we propose a multi-task architecture with separate task heads for segmentation and for lesion-severity evaluation. In this way, the segmentation DL model becomes a multi-task model capable of both precise lung/lesion segmentation and quantitative severity scoring; moreover, the segmentation outputs improve model interpretability for clinicians.

Using the above lung-segmentation model, we will compute the following quantitative metrics to characterize CT-detected disease burden:

- ① Absolute lesion volumes for the whole lung, each lobe, and each defined bronchopulmonary region.
- ② Percent lesion volumes for the whole lung, each lobe, and each bronchopulmonary region (i.e., lesion volume divided by region volume), used to quantify ARDS severity and lesion distribution.
- ③ Histograms of CT attenuation values (in Hounsfield units, HU) for different lesion regions.

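### LASSO coefficients that include non-randomised treatments are to be read as risk-driving factors across severity strata, with no clinical severity score named and no stability measure planned

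*Combined protocol and SAP*

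**What the plan says.** The last paragraph of the Statistical Analysis Plan, on mortality risk prediction, adds a LASSO regression "applied to all structural, pathological, and intervention-related variables". Its purpose is given in the same sentence: "standardized coefficients will be extracted to facilitate interpretation of key risk-driving factors across different ARDS severity strata". The variables are not itemised. The plan does not state the dataset, the choice of penalty, or whether each stratum has its own fit.

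Other sections bear on this:

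- The overall research design section describes a retrospective observational cohort, so treatment was chosen by clinicians.
- Data collection includes the SOFA and APACHE II scores. Neither is named for the LASSO.
- The section on the lung segmentation model defines regional lesion features. Its list of regions ends with "whole right, left upper-middle, left lower-middle, left lower, whole left, and whole lung", so aggregates stand beside their components.
- Sample size estimation allows "no more than 15 candidate predictors in the final multivariable logistic regression model" and asks for "at least 10 outcome events per predictor". It makes no allowance for severity strata.
- Interpretability, based on imaging-derived and clinical feature contributions, is a secondary outcome.

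**The concern.** A coefficient called risk-driving invites a causal reading. For treatments, this design does not support one: patients who receive more support are usually sicker, and the part of their severity that is outside the model is carried by the treatment variable. Treatments given mainly to less ill patients could look protective for the same reason.

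For imaging features the problem is reproducibility. When several inputs carry nearly the same information, LASSO keeps one and sets others to zero, and small changes in the sample alter which one is kept. The plan has no measure that would show this. Its five repeated experiments are reported as means and standard deviations of performance, not of coefficients.

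At stake is the plan's interpretability output. It could name factors that a second sample would not reproduce and list supportive treatments among the drivers of death, in a project whose primary objective includes helping to guide treatment.

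**Working it through.** **1. The plan's own figure.** Sample size estimation gives 15 predictors × 10 events = 150 deaths, and 150 / 0.375 = 400 patients. This reproduces the target exactly. The 37.5% is an in-ICU rate, whereas the outcome is 28-day in-hospital death; the steps below assume that it carries over.

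**2. Deaths available to the LASSO.** No dataset is named, so both candidates are shown.

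- All 400 patients: 150 deaths.
- The 276 training cases: 276 × 0.375 = 103.5 deaths, or 103.5 / 15 = 6.9 per predictor, already below 10.

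**3. Deaths per stratum, if strata are fitted separately (inferred).** Stratum shares are not given. With three equal strata and the same mortality in each:

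- All patients: 150 / 3 = 50.
- Training cases: 103.5 / 3 = 34.5.

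At 10 deaths per predictor these support 5 and 3 predictors. With assumed shares of 20/50/30% and assumed mortality of 20/35/53%, which average about 37.5%, the mild stratum has 400 × 0.20 × 0.20 = 16 deaths, or 276 × 0.20 × 0.20 = 11 in training.

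**4. Number of candidates (assumed, since the set is not itemised).** The smallest plausible set that includes the regional features has 11 regions with one lesion measure, the 6 anatomical features named for the concordance model, and the 5 interventions of the treatment-matching outcome: 11 + 6 + 5 = 22. (The protocol states 11 regions but lists 10.) With two lesion measures and three lesion types it is 11 × 2 × 3 + 6 + 5 = 77.

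| Deaths per candidate | 22 candidates | 77 candidates |
|---|---|---|
| All 400 | 150/22 = 6.8 | 150/77 = 1.9 |
| Equal stratum of 400 | 50/22 = 2.3 | 50/77 = 0.65 |
| Equal stratum of training | 34.5/22 = 1.6 | 34.5/77 = 0.45 |

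**5. Illustrative simulation.** All inputs are assumed. There were seven regional features, each loading 0.75 on a latent severity (pairwise correlation 0.56), plus whole right, whole left and whole lung; six anatomical features unrelated to outcome; and five treatments given more often to sicker patients. Part of severity lay outside the model. Mortality was 37.5%, the penalty was chosen by five-fold cross-validation, and each setting had 120 fits (60 pairs of samples).

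- Overlap: the variance inflation factor of the whole-lung value, given the other regional features, was about 5,000.
- Reproducibility: the regions selected in two independent samples overlapped (shared regions divided by all selected) by 0.21 at n=400, 0.18 at n=276 and 0.07 at n=133.
- Confounding: a treatment with no effect got a positive coefficient in 64% of fits at n=400, 57% at n=276 and 33% at n=133. With allocation unrelated to severity it was 7% at n=400 and 13% at n=276.

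**The case against.** The tempting stronger reading is that the analysis will flag treatments as harmful. The documents do not support that. The plan says that coefficients are to help interpretation; it claims no treatment effects and announces no reading of them as harm. The strength and direction of confounding are not given. In the simulation LASSO often dropped the treatment at small sample sizes, and a truly protective one (log odds ratio −0.4) was positive in only 8% of fits at n=276 and negative in 13%. The result is likely, not certain.

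Two premises are inferred. Results across strata could come from one pooled model displayed by stratum. The only structural features named near the LASSO sentence are the six anatomical ones, so entry of the regional aggregates is plausible but unstated. Both points stand, and the parts that depend on them are conditional. The treatment problem depends on neither. It needs only that the intervention-related variables include treatments actually received.

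Reading results within ARDS grade would remove some confounding, but three broad grades leave variation in illness within each.

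The overlap figures are partly built in: every region had the same loading, so there was no true ranking to recover. Nor are the aggregates the whole cause. In a separate run with similar assumed inputs, removing them raised the overlap of the top five features only from 17% to 26% at n=276. The figures illustrate the mechanism and do not predict this study's result.

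Finally, LASSO tolerates collinearity and many candidates when the aim is prediction. This is one supplementary sentence serving a secondary outcome.

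**Conclusion.** The concern holds as a fault of interpretation and specification that should be corrected. As written, the plan reads LASSO coefficients as drivers of risk although treatment is non-randomised, no clinical severity score is named among the inputs, and nothing measures selection stability or uncertainty.

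The size depends on what the plan leaves open. If strata are fitted separately and are equal, each has about 50 deaths in the full cohort or about 35 in training, against 150 planned for at most 15 predictors. If the regional features enter with their aggregates, the choice among them is largely arbitrary. The simulated rates hold only under their assumed inputs.

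A reader might infer that the mortality model or a primary outcome is undermined. It is not: no primary outcome rests on these coefficients.

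**What to change.** In the Statistical Analysis Plan:

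1. List the LASSO inputs, the dataset and the rule for the penalty.
2. Fit one pooled penalised model that includes ARDS severity and the SOFA and APACHE II scores already collected. Base any stratum-specific statement on prespecified severity interactions.
3. Enter either the regional lesion features or their aggregates, not both.
4. Bootstrap the whole procedure, penalty selection included, and report selection frequencies and the spread of the coefficients.
5. State that treatment coefficients will not be interpreted as effects. Leaving treatments out of the interpretive model alone is an alternative; the prediction model can keep them.
6. Replace 'risk-driving factors' by 'predictive markers' and label the analysis exploratory and associational.

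The cost is some wording and a bootstrap loop, with no new data. The downside is a less striking list and fewer statements about individual strata. Adding the severity scores reduces confounding by indication but does not remove it, so item 5 is needed even with item 2 in place.
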